16. DATA HANDLING AND RECORDKEEPING

16.1. Retention of Records

The investigator will maintain all study records according to ICH-GCP and applicable regulatory requirement(s). Records will be retained for at least 2 years after the last marketing application submission or 2 years after formal discontinuation of the clinical development of the investigational product. If the investigator withdraws from the responsibility of keeping the study records, custody must be transferred to a person willing to accept the responsibility. The Sponsor must be notified in writing if a custodial change occurs.

16.2. Case Report Forms

All case report form data will be entered in paper or electronic forms at the investigational site. A 21 CFR Part 11 compliant Electronic Data Capture system (EDC) will be used to capture data electronically for all subjects.

17. PUBLICATION POLICY

The Sponsor supports communication and publication of study results whatever the findings of the study.

[figure not shown]
The Sponsor reserves the right to review all planned communications and manuscripts based on the results of this study. This reservation of the right is not intended to restrict or hinder publication or any other dissemination of study results, but to allow the Sponsor to confirm the accuracy of the data, to protect proprietary information, and to provide comments based on information that may not yet be available to the study investigators. The Sponsor also encourages disclosure of any conflict of interest from all authors or investigators when manuscripts are submitted for publication. Those individuals, who have contributed greatly to this study, including lead external advisors and select principal investigators, may serve on any potential publications committee for the study.

18 APPENDICES

18.1 Appendix I: Registry for Screened and Not Randomized

For healthcare workers who have been screened and who would have qualified as eligible subjects but decline participation because of personal choice or logistical reasons, a registry will be offered with the same baseline data collection, schedule of NP sampling, and capture of outcomes. This will serve as a form of community surveillance for the medical center and will have a sample size that will not be pre-specified and limited only by the availability of NP COVID-19 sampling. For those who develop a positive NP test, the current guidance from the medical center administration and in concert with guidance from the U.S Federal Government, State and Local Authorities, Centers for Disease Control, and State and Local Health Departments, will all be applied in terms of next steps in monitoring and control of COVID-19 viral spread.

18.2 Appendix II: Cough Visual Analog Scale

18.3 Appendix III: Exposure Assessment Questionnaire

Exposure Questions		Visit:		Date		
#	Question	Details			Comments	
1	Number of shifts worked in the last 7d (in ICU/ED, +other COVID-19 unit)		Number of hours worked in last 7 d? (in ICU/ED, +COVID unit)			
2	Were you present in the room for a procedure likely to generate higher concentrations of respiratory secretions or aerosols ¹ ?	 no  yes	If yes:	List details (procedures, frequency, duration, etc.)		
3	Did you have extensive body contact with a +COVID-19 pt (e.g. rolling the patient, assisting in ADLs)?	 no  yes	If yes:	List details (activity, frequency, duration, etc.)		
4	Did you have prolonged close contact with a suspected/confirmed +COVID-19 pt (within 6 feet for > 15 min cumulatively in 1 or more shifts)?	 no  yes	If yes:	Were you in contact with secretions and/or excretions?	 no  yes	If Yes, did secretions contact unprotected:  Mouth  Eyes  Nose  hands

¹Examples: CPR, manual respiration, intubation, extubation, bronchoscopy, nebulizer therapy, or sputum induction

Staff initials: _____

Exposure Questions -continued			Visit:	Date
#	Question	Details	Comments	
5	Do you feel your PPE has been adequate?	 no  yes	If no:	Please describe:
6	Did you have unprotected exposures not described above (eg incomplete PPE for any duration with COVID19 patient):			

Staff initials: _____

From studies of viral shedding in patients with mild and more severe infections, shedding seems to be greatest during the early phase of disease. The role, if any, of asymptomatic carriers in transmitting infection is not yet completely understood. Pre-symptomatic infectiousness is a concern among healthcare workers and many countries are now using 1–2 days of symptom onset as the start day for contact identification.

Hydroxychloroquine and chloroquine are antimalarial agents that have been used for decades for both active treatment and prophylaxis. Several sources of data and rationale have been developed to support the notion that hydroxychloroquine may have activity against COVID-19.²

A prospective open-label trial from France evaluated the efficacy of hydroxychloroquine alone and in combination with azithromycin in symptomatic, hospitalized patients with positive COVID-19. The study composed of 36 patients, out of which 20 received 600 mg of hydroxychloroquine daily for 10 days. The remaining 16 patients who either refused the treatment or were not eligible to receive it because they were at other centers in France were considered as the control group. The primary endpoint was virological clearance of NP sampling at six days. Six patients who received hydroxychloroquine contributed incomplete NP sampling to the analysis because three worsened and were transferred to the intensive care unit, one patient died, one patient left the hospital, and one patient could not tolerate the study medication due to nausea. At day 6, 70% of hydroxychloroquine-treated patients were virologically cured comparing with 12.5% in the control group ($p= 0.001$). The investigators found the rate of recovery in patients taking hydroxychloroquine to be approximately 5 times more than that of patients in the control group.

Finally, research gaps about COVID-19 should be addressed in prospective, clinical trials as proposed in this study. The present study will leverage information concerning the infectious curve associated with COVID-19 exposure as illustrated in the figure.

2. Study design

This prospective open label trial will study the safety, tolerability, and efficacy of hydroxychloroquine in qualified health care workers. Qualified individuals will be administered hydroxychloroquine twice a day on day 1 (two 200 mg twice a day) and once a week (two 200 mg) afterwards for a total of 7 weeks. Dose de-escalation is permitted during the study if indicated clinically. All study individuals will follow the same visit and assessment schedule. Following study enrollment, participants will be scheduled to be assessed in person at Days 7, 14, 21, 28, 35, 42 and 49.

2.1. Sample size calculation

A total sample of 360 individuals (180 in each arm) would provide at least 80% power to detect a relative risk reduction of 40% in the rate of positive NP samples when the anticipated rate of positive conversion among those taking hydroxychloroquine is approximately 30%.

The power calculation, which was based on Pearson Chi Square test, assumes the following:

- One-sided Type I error rate of 0.05
- Anticipated positive NP samples rate of 30% in the clinical arm
- A 40% lower risk of a positive NP sample comparing the hydroxychloroquine group vs the controls
- Loss to follow-up rate of 15%

3. Aims and objectives

3.1. Objectives

For healthcare workers with

- One day or more of exposure to suspected and/or positive COVID-19 patients, including but not limited to those working in the Emergency Department or Intensive Care Unit.

OR

- Unprotected exposure to a known positive COVID-19 patient within 72 hours of screening.

3.2. Primary Objective

To assess the efficacy of hydroxychloroquine 400 mg twice a day (two 200 mg tablets twice a day) on day 1 followed by two 200 mg tablets once a week for a total of 7 weeks in the prevention of COVID-19 infection

3.3. Secondary Objective

To compare the rate of COVID-19 positive conversion among emergency department workers versus intensive care unit workers

4. Endpoints

4.1. Primary Efficacy Endpoint

Rate of COVID-19 positive conversion on weekly nasopharyngeal (NP) sampling

4.2. Secondary Efficacy Endpoints

Time-to-first clinical event consisting of a persistent change for any of the following:

- One positive NP sample
- Common clinical symptoms of COVID-19 infection including fever, cough, and shortness of breath
- Less common signs and symptoms of COVID-19 infection including headache, muscle pain, abdominal pain, sputum production, and sore throat

4.3. Exploratory Efficacy Endpoints

Time-to-first clinical worsening event consisting of any of the following:

- Hospitalization for COVID-19 infection
- Intensive care unit admission for COVID-19 infection
- All cause death

4.4. Safety Endpoints

Frequency, intensity, and relationship to study drug of adverse events and serious adverse events, change from baseline in body temperature.

5. Populations to be analyzed

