9.1.5. Management of COVID-19 positive test

If the result of an NP swab test demonstrates the presence of SARS-CoV-2, the subject will be directed to immediately receive appropriate medical care and will discontinue study treatment and procedures, however the sponsor will continue to follow the subject until their condition is resolved or death. Patient management following a positive test during the study will not be directed by study procedures and will be at the discretion of the subject's physician.

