5.2. Per Protocol (PP)

All randomised study subjects completing the whole study period (complete cases)

6. Analyses

All statistical analyses and data summaries will be performed using SAS® (Version 9.1 or higher) or other validated software. The SAP will serve as the final arbiter of all statistical analyses. Data will be summarized overall using descriptive statistics. Continuous data will be summarized with number of subjects (n), mean, median, minimum, maximum, relevant quartiles, standard deviation, coefficient of variation, and geometric mean (where applicable). Categorical data will be summarized using frequency counts and percentages. Chi Square or Fisher exact test will be used for comparing binary outcomes between treatment and control groups. Continuous variables will be compared between the study groups by means of two sample T test or Wilcoxon-rank-sum test.

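### The protocol conflicts on adverse-event follow-up after a positive swab; if section 9.1.5 is applied, crude AE proportions are distorted by conversion, in a net direction that is not known

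*SAP*

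**What the plan says.** **Safety endpoint.** SAP 4.4 lists "Frequency, intensity, and relationship to study drug of adverse events and serious adverse events", plus change in body temperature. The SAP has no safety analysis section. The only rules that reach AE data are the general ones in SAP section 6: counts and percentages for categorical data, and "Chi Square or Fisher exact test will be used for comparing binary outcomes between treatment and control groups". Nothing is said about person-time, censoring or an AE observation window.

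**AE collection.** Table 3 makes it a visit procedure, and Protocol 9.8.16 and 11.3 have AEs elicited by questioning at visits.

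**After a positive swab**, four sections bear on AE follow-up:

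- Protocol 9.1.5: the subject "will discontinue study treatment and procedures, however the sponsor will continue to follow the subject until their condition is resolved or death".
- Protocol 8.4.1: a positive test is a reason to stop study drug, and such subjects go on with all visits and assessments where possible. Section 8.4.2 does not list it as a reason to leave the study.
- Protocol 11.2.1.1: AEs are reported from the first dose to the final visit.
- Protocol 11.6: AEs are documented from the first dose until 49 days after the final dose, and AEs arising from concurrent illness are reportable.

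**Controls** have the same assessments apart from blood tests (Synopsis, Methodology) and take no study drug.

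**The concern.** Conversion is the primary efficacy outcome, and the design expects the groups to differ on it. If scheduled AE questioning stops at the swab, the group with more infections is watched for less time. A comparison of subjects with any AE would then differ between groups even if the underlying AE hazard were the same. The groups are self-selected (Protocol 7.3), so conversion could differ without any drug effect and still feed into the harm comparison.

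The other sections do not settle the matter. The 11.6 window depends on the final dose. For a treated subject whose last dose is the Day 42 dose it ends on Day 91 (42 + 49). For one who stops after the Day 7 dose because of a positive swab it ends on Day 56 (7 + 49). For a control neither the start (first dose) nor the end (final dose) exists, so the control window in 11.6 is undefined.

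**Working it through.** **The plan's own figure.** SAP 2.1 gives "A total sample of 360 individuals (180 in each arm) would provide at least 80% power". Its inputs are a one-sided 5% test, 30% conversion on hydroxychloroquine, a 40% relative reduction against controls, and 15% loss. Read literally, the control rate is 0.30/0.60 = 50% (not printed). Those inputs need 74 per group, 88 after dividing by 0.85, 176 in total; the 153 left per group after loss (180 × 0.85) give 97.5% power. The planned 360 follows instead if 30% is the control rate and 18% the drug rate (0.30 × 0.60): 156 per group, 180 after multiplying by 1.15, with 79.4% power at 153. Both pairs are carried below. The documents give no AE rate, so the background AE risk is an assumption, varied from 5% to 60%.

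**Mean AE observation if 9.1.5 is applied.** With a constant conversion hazard over 49 days and conversion risk p, mean time = 49p / (−ln(1−p)).

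- p = 0.50: 24.5/0.6931 = 35.3 days
- p = 0.30: 14.7/0.3567 = 41.2 days
- p = 0.18: 8.82/0.1985 = 44.4 days

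The treated-to-control ratios are 1.17 (30%/50%) and 1.08 (18%/30%). With observation ending at weekly swab visits, 30%/50% gives 42.3 versus 37.1 days, ratio 1.14.

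**Crude AE proportion, same true non-COVID hazard in both groups.** With background 49-day AE risk a, A = −ln(1−a) and C = −ln(1−p), the observed proportion is A/(A+C) × [1 − (1−a)(1−p)]. At a = 0.20, A = 0.2231:

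- p = 0.30: 0.2231/0.5798 × 0.440 = 16.9%
- p = 0.50: 0.2231/0.9163 × 0.600 = 14.6%
- p = 0.18: 0.2231/0.4216 × 0.344 = 18.2%

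| Background AE risk | Ratio, 30%/50% | Ratio, 18%/30% |
|---|---|---|
| 5% | 1.16 | 1.08 |
| 20% | 1.16 | 1.08 |
| 40% | 1.15 | 1.07 |
| 60% | 1.14 | 1.07 |

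At 20% background the spurious difference is 2.3 points (30%/50%) or 1.3 points (18%/30%). With 180 per group, a two-sided 5% test would then reject about 9.3% or 6.2% of the time with no true difference.

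**AEs clustered early.** If all AE hazard falls in the first 14 days, the ratio is 1.04 to 1.05 (30%/50%) or 1.02 (18%/30%).

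**COVID illness counted as an AE.** Let a share f of converters with no earlier AE have an illness AE recorded. This adds f × C/(A+C) × [1 − (1−a)(1−p)]. At 30%/50%, a = 0.20 and f = 0.5:

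- Treated: 16.9% + 0.5 × 27.1% = 30.5%
- Control: 14.6% + 0.5 × 45.4% = 37.3%
- Ratio 0.82

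The ratio passes below 1 when f exceeds about 12 to 13% at 20% background, or about 25 to 27% at 40% background, across both pairs of conversion rates.

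**If collection continues as in 8.4.1.** Both groups are observed for 49 days and the ratio for non-COVID AEs is 1.00.

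**The case against.** A reader might infer that AE observation simply ends at a positive swab. The documents do not establish that. It rests on one word in 9.1.5, whose own sentence keeps following the subject until resolution or death. Section 8.4.1 and both stated AE windows do not stop at the swab, and 11.2.1.2 requires SAE notification throughout the study regardless of drug administration. This stands: the distortion is conditional on 9.1.5. It does not dispose of the point, because the follow-up in 9.1.5 is tied to the infection and does not clearly restore routine AE questioning.

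A reader might also infer that the plan makes hydroxychloroquine look more toxic than it is. That holds only for non-COVID AEs under 9.1.5. Illness AEs are reportable and, at the plan's rates, commoner in controls, which can reverse the ratio. If visits continue under 8.4.1, the weeks off drug in treated converters would dilute a real drug effect, which is again the opposite direction.

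The crude comparison is itself inferred from a general rule, since SAP 4.4 specifies no between-group AE test. That is fair, but any-AE yes or no is a binary outcome, and this is the only method that the SAP supplies for one.

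Finally, the effect is modest beside the bias that self-selection can bring, and an AE rate per person-week is not a safe remedy. If AEs occur just after Day 1 the counts are nearly equal, and dividing by unequal time gives a rate ratio near 35.3/41.2 = 0.86, which favours the drug. Both points stand, and the second determines the fix.

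**Conclusion.** The concern holds in conditional form. The protocol gives incompatible accounts of AE follow-up after a positive swab, the 11.6 window is undefined for controls, and the SAP has neither an AE window nor a method that allows for unequal observation. If 9.1.5 is applied, crude proportions of non-COVID AEs are inflated in the treated group relative to controls by a ratio of about 1.14 to 1.16 at 30%/50% conversion and 1.07 to 1.08 at 18%/30%, the pair that reproduces 360. With AEs clustered in the first two weeks it is about 1.02 to 1.05, and with equal conversion it is nil. These figures assume constant hazards (except in the early-clustering case), AE risk unrelated to conversion within a group, and observation cut at conversion. Once COVID illness is counted, the net direction is not known. A crude proportion therefore cannot isolate drug harm, and no claim that the drug would look worse overall is supported.

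**What to change.** 1. Reconcile Protocol 8.4.1, 9.1.5, 11.2.1.1 and 11.6 on AE follow-up after a positive swab. Define one AE observation window, starting at enrolment or Day 1, that applies equally to both groups and does not depend on a dose date.
2. In SAP 4.4 and section 6, make the between-group comparison time to first non-COVID AE, shown as cumulative incidence, with censoring at the end of actual AE observation under the same rule in both groups. If collection does stop at the swab, conversion must enter as censoring (one minus Kaplan–Meier). Treating it as a competing event would return the same distorted proportions.
3. Report COVID-related AEs and AEs after a positive swab separately, by group.
4. Keep crude proportions, and any rate per person-week, as description only.

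The cost is protocol and SAP wording and a little more analysis, using visit, swab and AE onset dates that the study already records. The one drawback is that, if AE collection does stop at the swab, the comparison covers pre-conversion AEs only.

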5.1. Intention-to-treat (ITT)

- All subjects who received the study drug
- All subjects who participated in at least one post-baseline assessment

5.2. Per Protocol (PP)

All randomised study subjects completing the whole study period (complete cases)

6. Analyses

All statistical analyses and data summaries will be performed using SAS® (Version 9.1 or higher) or other validated software. The SAP will serve as the final arbiter of all statistical analyses. Data will be summarized overall using descriptive statistics. Continuous data will be summarized with number of subjects (n), mean, median, minimum, maximum, relevant quartiles, standard deviation, coefficient of variation, and geometric mean (where applicable). Categorical data will be summarized using frequency counts and percentages. Chi Square or Fisher exact test will be used for comparing binary outcomes between treatment and control groups. Continuous variables will be compared between the study groups by means of two sample T test or Wilcoxon-rank-sum test.

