7.3. Treatment Assignment

Qualified individuals may choose which group they want to be in. Subjects in the treatment group will receive hydroxychloroquine for 7 weeks. Those who decide to opt out of receiving treatments will compose the control group.

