8.4.1. Subject Discontinuation Criteria

Discontinuation refers to a subject's stopping administration of study drug. Reasons for study drug discontinuation may include the following:

- Confirmed clinical worsening event
- Occurrence of an AE or change in medical status that leads the investigator to be concerned about the subject's welfare
- Administrative reasons (e.g., inability to continue)
- Sponsor termination of the study
- Voluntary withdrawal
- Females who become pregnant during the study
- A positive COVID-19 test

Subjects who are discontinued from study drug should still continue in the study, completing all study visits and undergo all scheduled study assessments, if possible.

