8.4.2. Subject Termination Criteria

Termination refers to a subject's stopping study drug and all study assessments and visits. Reasons for study termination include the following:

- Loss to follow-up

- Death
- Withdrawal of consent

Every reasonable effort should be made to contact individuals who do not return for a scheduled visit. The investigator should inquire about the reason for withdrawal, request the subject return all unused investigational product, request the subject return for end-of-treatment and follow-up visits (if applicable), and follow up with the subject regarding any unresolved AEs.

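### The SAP's per-protocol set requires completing the whole study; if protocol 9.1.5 governs, a positive swab before Day 49 excludes the subject, so membership depends on the primary outcome

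*SAP*

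**What the plan says.** SAP 5.2, under the list of populations to be analyzed, defines the per-protocol set as "All randomised study subjects completing the whole study period (complete cases". It says nothing about subjects who have already had the primary event. SAP 6.1 takes that event to be at least one positive NP sample during the trial.

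The protocol describes what happens after a positive swab in two places:

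- Section 9.1.5: the subject "will discontinue study treatment and procedures, however the sponsor will continue to follow the subject until their condition is resolved or death".
- Section 8.4.1: "A positive COVID-19 test" is listed among the reasons to stop study drug, and then "Subjects who are discontinued from study drug should still continue in the study, completing all study visits and undergo all scheduled study assessments, if possible".

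Section 8.4.2 adds a third element: "Termination refers to a subject's stopping study drug and all study assessments and visits". The reasons it lists are loss to follow-up, death and withdrawal of consent. A positive test is not among them.

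On allocation, protocol 7.3 states: "Qualified individuals may choose which group they want to be in".

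**The concern.** A per-protocol set should be defined by adherence, not by outcome. Here the event being counted may itself end the procedures that count as completion. A subject who stays negative can complete the study. A subject who turns positive at Day 14 cannot, if 9.1.5 is followed. The set would then hold the never-positive subjects plus those first positive at the last swab, and its event proportion would describe little more than that last swab.

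The two protocol sections also differ in whom they cover. Section 9.1.5 speaks of any subject with a positive swab. The sentence in 8.4.1 concerns subjects taken off study drug, which untreated controls never take. If both sections were applied as worded, treated converters could remain in the set while control converters left it.

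Finally, no subject in this trial is randomised, so read literally the set is empty.

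**Working it through.** **Inputs.** Seven post-baseline swab visits, Days 7 to 49 (SAP 2). Planned size 180 per group, and a relative risk (RR) of 0.60 from the 40% reduction (SAP 2.1). The documents give no figure for the per-protocol set and no timing of conversions, so timing is an assumption.

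**Event rates.** SAP 2.1 puts 30% in the hydroxychloroquine group, which implies a control rate of 0.30/0.60 = 50%. On those rates, with a one-sided 0.05 test and 80% power, the chi-square calculation needs 74 per group, or 88 after 15% loss, well below the stated 180. Reading 30% as the control rate gives 30% × 0.60 = 18% on drug and 156 per group. That becomes 184 after dividing by 0.85, or 180 after multiplying by 1.15. The stated size fits the second reading better, so both pairs are carried through.

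**Who stays if 9.1.5 governs.** Only never-positive subjects and those first positive at Day 49. Let p be the proportion ever positive and L the proportion first positive at Day 49. The set is then a fraction 1 − p + L of the group, its event proportion is L/(1 − p + L), and the share of events removed is 1 − L/p.

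*Even timing:* L = p/7, so 6/7 = 86% of events leave.

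- p = 0.50: L = 0.0714, set 0.5714, proportion 12.5%.
- p = 0.30: L = 0.0429, set 0.7429, proportion 5.8%.
- p = 0.18: L = 0.0257, set 0.8457, proportion 3.0%.

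At 30% v 50% of 180 with no other loss, 54 and 90 converters become 7.7 and 12.9. About 123 of 144 events are removed.

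*Constant weekly hazard:* h = 1 − (1 − p)^(1/7) and L = (1 − p)^(6/7) × h, so the proportion in the set is simply h.

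- p = 0.50: h = 9.4%, 90% of events removed.
- p = 0.30: h = 5.0%, 88% removed.
- p = 0.18: h = 2.8%, 87% removed.

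| Rates (drug v control) | True RR | RR in set, even timing | RR in set, constant hazard |
|---|---|---|---|
| 30% v 50% | 0.60 | 5.8/12.5 = 0.46 | 4.97/9.43 = 0.53 |
| 18% v 30% | 0.60 | 3.04/5.77 = 0.53 | 2.80/4.97 = 0.56 |

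**Sensitivity to timing.** If between 5% and 30% of first positives fall at Day 49, between 95% and 70% of events leave the set.

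**If 8.4.1 governs.** Treated converters who keep attending stay, and none is lost because of the positive test.

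**If each section is applied as worded.** As a limiting case, every treated converter attends all visits and stays, and every control converter before Day 49 leaves. With even timing at 30% v 50%, the set compares 30% with 12.5%, an RR of 2.4, from the same true 0.60.

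**The case against.** The strongest reply is that nothing in the plan uses this set. SAP 6 and 6.1 assign it no comparison. The primary population is defined by having received at least one dose, the SAP's intention-to-treat definition does not require completion, and the synopsis speaks of intent-to-treat throughout. This stands. A reader might infer that the primary efficacy result is biased; the documents do not support that.

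A reader might also infer that the set certainly loses nearly every case. That holds only if 9.1.5 governs. Section 8.4.2 does not make a positive test a reason for termination, and 8.4.1 keeps converters in the study where possible. The phrase about complete cases could also mean no missing outcome, and a converter's outcome is known. These points make the removal conditional. They do not cure the definition, because it also requires completing the whole study period, and the follow-up to resolution or death in 9.1.5 is not the scheduled visits and swabs.

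Three smaller inferences also fail:

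- The set would not vary from site to site. The synopsis says single center, so any inconsistency would lie between staff, subjects or groups.
- The clinical endpoints are not clearly damaged. The secondary endpoint is time to first event and counts a positive swab, so later symptoms would generally not change it. Hospitalization, intensive care and death fall within the follow-up that 9.1.5 keeps.
- An RR of 0.46 is not the expected distortion. It is the most extreme of the four scenarios tabulated.

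**Conclusion.** The definition is defective and should be corrected, but the consequence is conditional and confined to per-protocol results. If 9.1.5 governs, membership depends on the primary outcome. About 86–90% of events leave, and a true RR of 0.60 appears as about 0.46–0.56, so the exclusion alone exaggerates the benefit. If 8.4.1 governs, treated converters can stay, but its wording leaves controls uncovered, so exclusion could differ by group.

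The percentages rest on assumed timing (even or constant hazard over seven swabs, the same pattern in both groups) and on no other outcome-related loss. The set is named among the populations to be analyzed, so a per-protocol sensitivity result is foreseeable, and as written it could neither support nor challenge the primary result. The word randomised is an error whichever section governs.

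**What to change.** In SAP 5.2:

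- Delete the word randomised.
- Count a subject in either group as completing when followed with the scheduled NP swabs to the first positive result or Day 49, whichever comes first.
- For treated subjects, apply the compliance threshold in protocol 9.4 (not compliant if more than 25% of expected doses are missed) to doses due up to that point. State that this adapts 9.4, which counts all expected doses.
- State which analysis, if any, uses the set.

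In the protocol, reconcile 8.4.1 and 9.1.5 in one statement, the same for both groups, on which study assessments continue after a positive swab. This review takes no position on which of the two rules is right.

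The cost is a few sentences, with no added subjects or procedures. There is one small downside: an early converter needs fewer swabs to qualify than a subject who stays negative, so missed swabs should be reported by group.
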